This study is a modification of classical experimental gingivitis model. The study will prospectively enroll subjects and a maxillary sextant to an intervention, while the other sextant will serve as control in a split-mouth design of localized experimental gingivitis, utilizing localized stent-induced biofilm overgrowth model (SIBO). The intervention will consist of cessation of oral hygiene versus an active control of oral hygiene with a fluoridated toothpaste that will be provided by the investigators. The intervention, i.e. oral hygiene cessation will manipulate the participants' oral environment by leading to reversible inflammation of the gingival tissues. This is a well established protocol that was first introduced in 1965 (Loe's experimental gingivitis) and is safe, reliable and widely utilized in periodontal clinical trials. The purpose of this study is to evaluate the effects of oral hygiene cessation in the gingival tissues by an innovative non-invasive microimaging technique, i.e. OCT.

The study will include the following phases – 1) Hygiene phase of 2 weeks; 2) Gingivitis induction phase with stent lasting up to 2 weeks; and 3) Resolution phase of 2 weeks. This pilot study will enroll up to 15 generally healthy adults aged 18-35 years that are self-referred or referred to the UW School of Dentistry. Recruitment will be completed in 3 waves. The study will include an oral health history review, probing depths, plaque & gingival evaluations, biospecimens collection and imaging of the buccal gingiva of teeth #5 - 12.

RECRUITMENT

All study participants will be patients of record at the UW School of Dentistry, or referred. All study participants will undergo informed consent process, prior to enrollment in the study. Categorization of participants and sites will be based on the clinical assessments. Other than the study-related oral health history recorded, there is no intention to obtain information from the participants' other dental or medical records. The first participant will be assigned a number, and all the following subjects will be assigned consecutive numbers by accession.

Inclusion criteria:

- Aged 18-35 years
- In good general health, ASA I
- No clinical signs of gingival inflammation at >90% sites observed
- Probing Depth(PD) \leq 3.0 mm
- Attachment Loss (AL) = 0 mm
- Gingival health at baseline visit (Day 0): Gingival Index (GI) \leq 0.5, Bleeding on probing (BOP)(-)
- Non-smokers
- Fluent in English

Confidential

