Exclusion criteria:

- Medical condition which requires premedication prior to dental treatments/visits
- Subjects unable or unwilling to undergo informed consent process.
- Subjects currently using anti-gingivitis oral rinses (washout period of 1 week)
- History of periodontal disease
- History of systemic inflammatory or immune conditions
- Use of antibiotic or anti-inflammatory drugs within 30 days of enrollment
- Pregnant or breastfeeding at time of screening
- Concurrent orthodontic treatment
- Untreated carious lesions and/or inadequate restorations, implants, crowns on maxillary non-molar teeth
- Participation in any other clinical study or test panel within 1 week prior to enrollment into this study
- Use of tobacco products
- Subjects who must receive dental treatment during the study dates
- Orthodontic bands, appliances, or crowns and bridges, or removable partial dentures affecting the non-molar maxillary teeth
- Immune compromised individuals (HIV, AIDS, immuno suppressive drug therapy)

[figure not shown]
METHODS

Induced Gingivitis Model

In each participant, one maxillary quadrant will be assigned as test quadrant (experimental gingivitis) and contralateral quadrant as control quadrant. Assignment of quadrants will be random using a computer program for randomization.

At the initial visit all participants will undergo the informed consent process, with thorough discussion of study participation details. Full clinical assessments, biospecimen collections and imaging will be performed and maxillary impression will be taken for acrylic stent. Maxillary acrylic stents will be fabricated to cover teeth on test quadrant extending at least 4-5 mm apical to the marginal gingiva both buccal and palatal and will be relieved around interproximal areas to prevent plaque disturbance. An oral prophylaxis will be administered and thorough oral hygiene instructions will be given. Participants will return 14 days after this initial visit and will have baseline measurements and biospecimen collections taken. These measurements include an abbreviated health assessment with a periodontal probe to measure pocket depths, gingival and plaque index and Imaging of the buccal gingival on eight maxillary teeth (#'s 5-12), and collection of crevicular fluid and plaque samples³⁷.

UW - Colgate Imaging Study

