In the present study, we will be examining the sensitivity, specificity, and practicality of a new microimaging technique for assessing experimental gingivitis, as compared with standard health-related biomedical outcomes (i.e. gingival index and gingival crevicular fluid volume).

Abbreviated periodontal health assessment

Clinical data will be documented based on probing depth (PD), visible plaque index (VPI), gingival index (GI) and bleeding on probing (BOP)³⁸. All clinical measurement will be conducted using a manual periodontal probe. BOP will be recorded within 20 seconds of probing. The following four maxillary teeth will be used in each test and control quadrant: first premolar – central incisor. For each tooth, all measurements and biospecimen collection will be taken on mesiobuccal and mesiopalatal surfaces. Staggering of sites (mesiobuccal & mesiodistal) will be performed for plaque collection.

Visible Plaque Index

The surfaces of the study teeth will be scored and given either a "0" no plaque or "1" plaque assessment:

0 = No plaque

1 = Visible Plaque

Confidential

Loe and Silness Gingival Index (GI)

The surfaces of the study teeth will be evaluated using light air and a periodontal probe. A score is given based on the following scale:

0 = Normal gingiva

1 = Mild inflammation, slight change in color, slight edema, no bleeding on probing

2 = Moderate inflammation, moderate glazing, redness, bleeding on probing

3 = Severe inflammation, marked redness and hypertrophy, ulceration, tendency to spontaneous bleeding

Gingival Crevicular Fluid (GCF) collection

Prior to GCF collection the plaque index will be recorded. The sites to be sampled will be isolated with cotton rolls and gently air-dried. GCF samples will be collected with sterile paper strips (Periopaper strips, Oraflow Inc.) that will be inserted into the gingival crevice until mild resistance is felt and left in place for 30 seconds.

Amount of GCF samples collected will be quantified with a Periotron 6000 (Oraflow, Inc.) and will be expressed in microliter.³⁹ GCF will be collected from the mesiobuccal and mesiopalatal surfaces of teeth #'s 5- 12. Paper strips visibly contaminated with saliva and blood will be excluded from the study. All samples will be collected in micro centrifuge tubes. They will be transported on ice and stored within 24 hours at -80oC until processing.

Plaque collection

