A label with the subject's ID and the date of preparation is affixed to the buccal surface, and then 1-mm-thick mouthguard material is vacuum-adapted over the toothshield and trimmed to the original contours. The shields are prepared prior to the prophylaxis, chemically disinfected, and packed in individual plastic bags with each subject's name.

Statistical Analysis Plan

Multiple sites within each subject will be evaluated using a Gingival Bleeding Index at baseline and subsequent timepoints during clinical exams. The gingivitis bleeding scores will be averaged to provide a mean score per subject for each exam period. Product means and standard deviations will be calculated for each time period. Analysis of Variance techniques (possibly including Analysis of Covariance using the baseline scores as the covariant) will be used to compare the difference between the two test treatments using the 95% confidence level ($p \leq 0.05$).

Based upon our initial study the selection of 15 participants is expected to identify statistically significant differences in clinical parameters, GCF chemokines level, MPO expression and microbial composition over time among the subjects of the study. Participants will be enrolled in cohorts of 5 and we have planned for 3 waves to reach the final sample size $N=15$.

Confidential

REPORT OF ADVERSE REACTIONS

Subjects will be told of any possible adverse reactions or side effects from lack of oral hygiene and stent use, i.e. oral irritation. At the all clinic visits/examinations each participant will be asked if they have experienced any discomfort or oral irritation. In addition, all subjects will be examined for signs of epithelial desquamation (sloughing) and discoloration of the teeth and/or tongue. The investigators will record any and all adverse reactions. If the evidence indicates that the adverse reaction may be due to lack of oral hygiene, the subject will be instructed to resume oral hygiene and appropriate treatment will be provided. If an adverse event occurs it is expected to be mild and abate (stop) when oral hygiene is resumed. In the event of an adverse experience, emergency or other problems or questions regarding participation in this study subjects will be advised to contact the following investigator(s):

[name]
Office: [contact]

In the event of a medical emergency, subjects will be instructed to contact their physician.

Definitions

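### The SAP averages bleeding scores to one mean per subject and names no within-subject comparison, although test and control are two quadrants of the same mouth

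*Combined protocol and SAP*

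**What the plan says.** The design is within-subject. Study Design describes one side of the upper jaw receiving the intervention, "while the other sextant will serve as control in a split-mouth design of localized experimental gingivitis". Under Methods, Induced Gingivitis Model, in each participant "one maxillary quadrant will be assigned as test quadrant (experimental gingivitis) and contralateral quadrant as control quadrant", and "Assignment of quadrants will be random using a computer program for randomization". So quadrants are randomised and participants are not. Under Outcomes, Abbreviated periodontal health assessment, the measurement scheme is by side: "The following four maxillary teeth will be used in each test and control quadrant", with two surfaces scored per tooth.

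The Statistical Analysis Plan reduces the data differently. Scores from multiple sites are combined: "The gingivitis bleeding scores will be averaged to provide a mean score per subject for each exam period". Next, "Product means and standard deviations will be calculated for each time period". The method is analysis of variance, perhaps with the baseline score as a covariate, and the plan says that it "will be used to compare the difference between the two test treatments", at the 5% level. The section does not mention quadrant, split-mouth, pairing, a subject block, a random effect or repeated measures, and no other section supplies them. The sample size is 15 participants, without an effect size, SD, power or within-mouth correlation.

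**The concern.** The averaging unit does not fit the unit of randomisation. A mean per subject is a sensible unit when whole participants are allocated to different products. Here no products are compared: every participant gets the same toothpaste, and the contrast is hygiene cessation on one side against continued hygiene on the other. One mean per participant holds both conditions and leaves no treatment factor to test.

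An analyst who sees this and forms quadrant means must still choose a model, and the paragraph does not say that the two means from one mouth belong together. An ordinary two-group ANOVA would treat 15 test and 15 control quadrants as 30 independent units. That gives up the main statistical advantage of a split-mouth study, in a pilot of at most 15 people who each undergo induced gingivitis. It also leaves the choice of analysis open until the data are in hand.

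**Working it through.** **The plan's own figure.** N = 15 cannot be reproduced, because the documents give no effect size, SD, power or correlation. What follows shows the consequences of the wording under stated assumptions.

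**Reading 1: one mean per subject and visit.** From baseline on, each quadrant has 4 teeth × 2 surfaces = 8 sites (Outcomes; Appendix B). With quadrant means T and C, the subject mean is

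(8T + 8C)/16 = (T + C)/2.

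The contrast T − C cannot be recovered from (T + C)/2. If hygiene cessation raises T by D and leaves C unchanged, the subject mean rises by D/2. That is visible only as change over time, without the concurrent control the design provides. No between-treatment comparison is left for the ANOVA.

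**Reading 2: quadrant means, ordinary two-group ANOVA.** Inputs: 15 pairs (from the SAP); two-sided 5% level (two-sided is assumed); equal SD σ in both quadrants, within-mouth correlation ρ and difference d in units of σ (all assumed); no dropout (assumed).

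- Unpaired standard error: σ√(2/15) = 0.365σ.
- True (paired) standard error: σ√(2(1 − ρ)/15).
- Ratio of the two: 1/√(1 − ρ).

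Type I error was found by simulating 400,000 trials per setting with no difference. The unpaired test has 28 degrees of freedom and the paired test 14.

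| ρ (assumed) | Paired SE | Unpaired SE ÷ paired SE | Type I error, unpaired | Type I error, paired |
|---|---|---|---|---|
| 0 | 0.365σ | 1.00 | 5.0% | 5.0% |
| 0.3 | 0.306σ | 1.20 | 2.2% | 5.0% |
| 0.5 | 0.258σ | 1.41 | 0.8% | 5.0% |
| 0.7 | 0.200σ | 1.83 | 0.1% | 5.0% |

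Power from the same simulation:

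| ρ | d | Unpaired | Paired |
|---|---|---|---|
| 0 | 0.7 | 46% | 43% |
| 0.5 | 0.5 | 20% | 44% |
| 0.5 | 0.7 | 44% to 45% | 71% |
| 0.5 | 1.0 | 82% | 95% |
| 0.5 | 1.5 | above 99% | above 99% |

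The loss grows with ρ and vanishes for very large effects. At ρ = 0 the paired test is slightly weaker, because it has fewer degrees of freedom.

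**Reading 3: quadrant means, ANOVA with subject as a block.** At a single visit this is the paired t-test (F on 1 and 14 degrees of freedom equals t²) and is valid. The SAP does not state it, and it needs quadrant means, which the averaging sentence does not provide.

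**The case against.** The best defence is to read the paragraph as a whole. A mean pooled over both quadrants could feed neither the summaries by product nor a comparison of two treatments. The authors therefore probably meant a mean per subject under each condition, and the product wording looks like a borrowed label. The phrase about analysis of variance techniques is also broad enough to cover a blocked or repeated-measures ANOVA. Both points stand: the plan does not forbid a correct analysis. But the reader has to supply both the averaging unit and the pairing, and the one unit the text does give is wrong for the design.

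Second, an unpaired test errs on the safe side when ρ is positive, and a large induction effect might be found anyway. That also stands, and it limits the harm to lost power. It does not help Reading 1, which fails whatever ρ is. Nor can it be relied on for the GCF chemokines and MPO, where the SAP also expects differences but gives no effect sizes.

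Third, averaging sites is not itself a fault. Agreed: it avoids counting sites as independent. It should stop at the quadrant.

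A reader might go further and infer that the visits will be stacked as independent observations, which would inflate false positives. The documents do not support this. The SAP summarises by exam and by time period, and nothing says visits are pooled as separate rows. Any figure for such inflation would also need variance shares that the documents do not give.

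**Conclusion.** The point holds as a mismatch between design and analysis plan. Read literally, the SAP's summary measure cannot yield the comparison the SAP names; this rests on no numerical assumption. Under the next reading, an unpaired ANOVA on quadrant means, the test is conservative for positive ρ: true type I error falls from 5% to between about 2% and 0.1% as ρ goes from 0.3 to 0.7. The power cost at ρ = 0.5 is about 26 percentage points at d = 0.7 (71% less about 45%) and 13 at d = 1.0 (95% less 82%). These sizes are illustrations, since ρ and d are assumed.

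Two stronger conclusions are tempting but not supported. One is that the plan prescribes an invalid test: it is silent on pairing, and its wording admits a blocked ANOVA. The other is that the contrast is lost for good: measurements are taken by tooth and surface, so quadrant means can still be formed.

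**What to change.** Rewrite the analysis paragraph of the SAP:

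1. Average sites to one mean per subject, quadrant and visit.
2. Compare test with control within subject, and state which method is used. One option is a paired test on the test-minus-control difference at a given visit. The other is a linear mixed model over visits, with fixed quadrant, visit and quadrant-by-visit, and random subject and subject-by-quadrant. These are different analyses: the model pools variance over visits and uses incomplete data differently.
3. If a baseline covariate is used, take it from the same quadrant.
4. Replace the product and two-treatment wording with test quadrant and control quadrant.

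Naming one key visit is optional. If Day 14 is named, the SAP should say how the analysis handles participants moved early to the resolution phase under Recovery and Termination from the Study, since Day 14 is not the end of induction for them. Using the last induction-phase visit is one possibility.

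The cost is SAP wording only. Visits, measurements and sample size are unchanged.

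### The SAP tests an undefined Gingival Bleeding Index and specifies no analysis of the gingival index or GCF volume, the protocol's own standards

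*Combined protocol and SAP*

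**What the plan says.** The Statistical Analysis Plan section states: "Multiple sites within each subject will be evaluated using a Gingival Bleeding Index at baseline and subsequent timepoints during clinical exams". It continues: "The gingivitis bleeding scores will be averaged to provide a mean score per subject for each exam period". The stated method is analysis of variance, "possibly including Analysis of Covariance using the baseline scores as the covariant". On its purpose and significance level, the section says that this method "will be used to compare the difference between the two test treatments using the 95% confidence level". It gives no scale, scoring rule or list of sites for this index. The next paragraph of the section expects 15 participants to show differences in clinical parameters, GCF chemokines, MPO and microbial composition, but attaches no model to any of them.

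The Outcomes section says that the imaging technique will be judged against "standard health-related biomedical outcomes (i.e. gingival index and gingival crevicular fluid volume"). Under the abbreviated periodontal health assessment, "Clinical data will be documented based on probing depth (PD), visible plaque index (VPI), gingival index (GI) and bleeding on probing (BOP"). For bleeding, the only recording rule is: "BOP will be recorded within 20 seconds of probing". The GI is defined there on a 0 to 3 scale: 0 is normal, 1 is mild inflammation without bleeding on probing, and bleeding on probing enters at 2.

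The inclusion criteria require GI of at most 0.5 and negative BOP at the Day 0 baseline visit. A separate line, with no visit attached, asks for no signs of inflammation at more than 90% of observed sites. Appendix B lists GI, BOP and GCF as separate items at Days -14, 0, 2, 4, 7, 14, 21 and 28.

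**The concern.** The only outcome with a specified test goes by a name that appears nowhere else in the protocol. It could mean a proportion of BOP-positive sites, the GI, or a third instrument. These are different outcomes, and the plan leaves the choice open until after the data have been seen.

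The two measures that the protocol holds up as its reference have no specified analysis. If the SAP score is read as bleeding-only, mild inflammation does not register in it, although the stated aim is to assess how much inflammation is present and how it resolves.

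A smaller question follows from eligibility. If nobody may bleed at baseline, adjusting for baseline bleeding may achieve nothing.

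**Working it through.** **1. The plan's own figures.** The 95% confidence level and the p-value threshold agree: 1 - 0.95 = 0.05. The sample size of 15 cannot be reproduced, because no effect size, standard deviation or power is given. Nothing below depends on it except the row count in step 4.

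**2. The sections side by side.**

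| Outcome | Defined | In Appendix B | Named as a standard in Outcomes | Analysis specified in SAP |
|---|---|---|---|---|
| Gingival Bleeding Index | No | Not under that name | No | ANOVA, optionally ANCOVA |
| GI | Yes, 0 to 3 | All 8 visits | Yes | No |
| BOP | Timing rule only | All 8 visits | No | No, unless it is what the SAP means |
| GCF volume | Yes, collection and quantification | GCF at all 8 visits | Yes | No |

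**3. What a bleeding-only score can register.** Each quadrant has 4 teeth x 2 surfaces = 8 sites, so a subject has 16. Score a site 1 if it bleeds on probing and 0 if not. On the protocol's scale, GI 0 and GI 1 are both non-bleeding. If k of the 8 sites in a quadrant move from GI 0 to GI 1:

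- change in quadrant-mean GI = k/8
- change in quadrant-mean bleeding score = 0

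With k = 4 the changes are 0.5 and 0; with k = 8 they are 1.0 and 0.

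**4. The optional baseline covariate.** With 15 subjects and 2 quadrants there are 30 rows. The columns are intercept, treatment and baseline (3), or 17 once 14 subject indicators are added. The result depends on what the baseline score is taken to be.

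- *Bleeding-only, with BOP-negative meaning every site.* Every baseline score is 0. The rank is 2 of 3 columns (16 of 17 with subject effects), so the baseline slope cannot be estimated. The column drops out and leaves the treatment estimate unchanged; in one simulated data set it was 0.9104 with and without the covariate.
- *Bleeding-only, with fewer than 10% of the 16 sites allowed to bleed.* Since 15/16 = 93.75% passes and 14/16 = 87.5% fails, at most one site may bleed. The subject mean is 0 or 1/16 = 0.0625, and the quadrant mean is 0 or 1/8 = 0.125. The design has full rank once any subject has such a site, but the covariate is almost degenerate.
- *The score is the GI, with subject mean at most 0.5 and no bleeding.* Sites score 0 or 1, and up to 8 of 16 may score 1. The mean can take 9 values from 0 to 0.5, and the covariate is estimable.

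**5. Would Day 0 GI be a useful covariate?** Not certainly. The criteria do not say whether the 0.5 limit applies per site, quadrant or subject; applied per site, whole-number scores would force every value to 0. If the 90% criterion applies to the 16 study sites at Day 0, at most one site is inflamed and the quadrant-mean GI is 0 or 0.125.

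**The case against.** The strongest reply is that this is loose naming. BOP is collected at every scheduled visit, the SAP speaks of averaging bleeding scores over sites, and one sentence defining the score from BOP would close the gap. GI and GCF are recorded in any case, and the sample-size paragraph shows that the authors expected to look at clinical parameters generally. ANCOVA is only a possibility, and a constant covariate is harmless.

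Much of this stands, and it rules out four stronger readings that a reader might infer:

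- *The endpoint is not collected.* The documents do not support this. The name is undefined, but bleeding is recorded and a score can be derived from it.
- *Eligibility makes the ANCOVA covariate constant.* This needs a bleeding-only score, BOP-negative at every site, and no exceptions. The criterion states no site or subject level, and the section on adherence to the protocol allows case-by-case eligibility waivers. Even where it holds, nothing is biased or invalid.
- *A floor at zero breaks the equal-variance assumption of ANOVA.* The documents give no bleeding data. In a split-mouth design, a test on within-subject differences does not need equal variances in the two quadrants.
- *The device is meant specifically to detect GI 1.* The aim speaks of the level of inflammation and its resolution; it does not single out that grade.

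The reply leaves two things unanswered. Defining the score from BOP would supply a definition, but the SAP would still give no analysis of the outcomes that the protocol names as its standards, and a bleeding-only score would still miss mild inflammation. A general reference to clinical parameters in a sample-size sentence is not an analysis, and GCF volume is not mentioned there.

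**Conclusion.** The point holds as a mismatch between the SAP and the protocol. The one outcome with a specified test is undefined, and neither of the two named standards has a specified analysis. This part rests only on reading the sections together.

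The loss of information is conditional on the score being bleeding-only. In that case every change between GI 0 and GI 1 contributes exactly zero, whatever its frequency. How often such changes would occur cannot be said from the documents.

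The covariate point is secondary and conditional. On the strictest reading the precision gain is nil; on the looser bleeding reading the covariate is nearly degenerate; if the score is the GI it can vary. On no reading does it bias the treatment comparison.

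**What to change.** In the Statistical Analysis Plan section:

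- Replace the per-subject mean Gingival Bleeding Index with the mean GI per quadrant (test and control) at each visit, as the main clinical endpoint. Compare the quadrants within subject, since each participant supplies both conditions.
- Make the proportion of BOP-positive sites and GCF volume secondary endpoints, each with a stated within-subject analysis.
- Do not rely on a bleeding baseline for ANCOVA. If a baseline term is wanted, use the quadrant's Day 0 GCF volume. Day 0 GI is possible but may vary little (step 5).
- State whether BOP-negative at Day 0 applies to every site, and at what level the GI limit applies.

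The cost is SAP wording. GI, BOP and GCF are already scheduled at every visit, so no procedure or visit is added. The one drawback is that the GCF section excludes strips visibly contaminated with blood, so some GCF values may be lost, possibly more often at bleeding sites. The number of excluded strips should be reported by quadrant and visit.

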Participants in this study will receive up to \$500 in gift cards for their participation. A \$50 gift card will be given at the end of each visit, and subjects who attended all study visits will receive an additional \$100 gift card at the final visit (28-day visit). Payment will be prorated for visits attended only. No therapeutic or other benefit will be received by participating in the study.

QUALITY ASSURANCE/CONDUCT OF THE STUDY

This clinical research study will be conducted in compliance with this protocol and U.S. Federal Regulations governing informed consent (21 CFR 50), Institutional Review Board (21 CFR 56), applicable regulations governing Investigator conduct (21 CFR 312) and/or any local regulatory agency (where applicable).

It is the responsibility of the Investigator to ensure that all subject data are collected and reported according to the study protocol. Subject records will indicate subject and examination information such as visit dates, examiners, etc. that is unique to this study and the subjects. Proper documentation of all adverse events and final resolutions will be maintained. Case report forms will be used for recording all clinical data. All CRFs used in this study will be provided by the study sponsor. The Investigator will be responsible for maintaining original consent forms, case report forms (CRFs), and other source documentation.

Data Management Responsibilities

Data collection is the responsibility of the clinical research site staff under the direction of the Principal Investigator. The Investigator will keep a copy of every document (clinical and laboratory) related to the research study.

Data generated at the clinical site will be transferred to the sponsor by the Co-Investigator via mail or electronic email for statistical analyzes. The principal Investigator and study manager are responsible for the review and interpretation of the analyzed data.

Subject Termination/Procedures

A genuine effort will be made to determine the reason(s) why a subject fails to return for the necessary visit(s) or is dropped from the study. Subjects could be dropped from the study if any of the following occur:

1. Subject fails to substantially comply with the protocol requirements.

Confidential

2. Subject fails to report for a scheduled examination.
3. Subject is treated with medications during the course of the study, which may interfere with the parameters of the study.

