The Investigator will be required to adhere to the final protocol. Any changes to the protocol, except those necessary to eliminate apparent hazards, will require prior approval by the local reviewers through the submission of a protocol amendment. These changes to the protocol must be implemented only through formal written protocol amendments and only upon joint approval by the sponsor and investigator. If a protocol amendment requires changes to the informed consent form, the revised consent form must also be approved by any local board. Departures from eligibility requirements may be allowed on a case-by-case basis by the medical monitor or other authorized sponsor representative.

Such departures must be medically and scientifically justified, must be pre-authorized, and must be documented in the case report form and tracked as official eligibility waivers.

Institutional Review Board

Prior to initiation of the study, the Investigator will obtain Institutional Review Board approval for the study protocol, the informed consent document, study instructions, and any forms of advertising in compliance with regulations. The IRB will review the investigation at least once a year and will review any significant change in the protocol before the change is initiated. The Investigator will maintain all

Confidential

original correspondence. IRB approval for this study will be obtained from:

Human Subjects Division
University of Washington [name]
[name]
[contact]

Advertising

No newspaper, radio, or television advertising will be used for recruitment purposes. A flyer will be created to recruit participants. The flyer will be approved by an Institutional Review Board prior to posting or dissemination.

Informed Consent Process

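### The eligibility-waiver clause exempts no criterion, not even Day 0 gingival health, and the analysis plan does not say how waived subjects are handled

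*Combined protocol and SAP*

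**What the plan says.** Three provisions in Adherence to Protocol/Amendment(s) bear on this point.

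- Adherence: "The Investigator will be required to adhere to the final protocol".
- Amendments: apart from hazard removal, changes need prior approval by the local reviewers, and "These changes to the protocol must be implemented only through formal written protocol amendments and only upon joint approval by the sponsor and investigator".
- Waivers: "Departures from eligibility requirements may be allowed on a case-by-case basis by the medical monitor or other authorized sponsor representative". The next sentence sets conditions: "Such departures must be medically and scientifically justified, must be pre-authorized, and must be documented in the case report form", and they are to be "tracked as official eligibility waivers".

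The Institutional Review Board section adds that the board "will review any significant change in the protocol before the change is initiated". The waiver sentences do not mention the board, the local reviewers or the investigator.

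Among the inclusion criteria, the item opening "Gingival health at baseline visit (Day 0): Gingival Index (GI" sets an upper limit of 0.5 for GI and requires negative bleeding on probing (BOP). The exclusion criteria include systemic inflammatory or immune conditions, immune compromise, a need for premedication, and recent antibiotic or anti-inflammatory use. Pregnancy is on that list too, but the Pregnancy section separately rules out knowingly enrolling a pregnant woman.

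The Statistical Analysis Plan averages bleeding scores per subject and visit and compares the two treatments by analysis of variance. Analysis of covariance on baseline is mentioned only as a possibility. The plan defines no analysis population and no handling of waived subjects.

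**The concern.** The study aim is to follow gingival inflammation as it is induced and as it resolves, so Day 0 has to be a healthy reference state. The Day 0 criterion secures that, and as written it can be set aside for an individual subject by a decision on the sponsor's side.

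Two things are at stake. The first is interpretation: a subject admitted with bleeding sites starts induction already partly in the state that the model is meant to create, and this occurs on the bleeding outcome that the plan analyses. The second is protection: the Compensation section says that subjects gain no therapeutic benefit, so waiving a medical exclusion has no offsetting benefit to that person.

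**Working it through.** **Reach of the clause.** It refers to eligibility requirements in general and lists no exceptions. Day 0 gingival health is one of the inclusion criteria, so it is covered. The medical exclusions are covered in the same way, except that pregnancy has its own bar.

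**What a waived Day 0 looks like.** On the Löe and Silness scale in the protocol, GI 1 excludes bleeding on probing and GI 2 includes it. A bleeding site is therefore GI 2, moderate inflammation, before oral hygiene stops. There are 8 teeth × 2 surfaces = 16 sites per subject (Appendix B). The protocol does not say whether the 0.5 limit is a subject mean or a per-site limit; a subject mean is assumed here. With bleeding sites at 2 and all others at 0:

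- one bleeding site: 2/16 = 0.125
- four bleeding sites: 8/16 = 0.5

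On this reading a subject with up to four bleeding sites still meets the GI limit and fails only on BOP. BOP negativity is then the part of the criterion that guards the healthy start.

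**Share of the sample.** N = 15, in three waves of 5. For k waived subjects the share is k/15: 1/15 = 6.7%, 2/15 = 13.3%, 3/15 = 20.0%. The documents give no expected number of waivers, so k is an assumption.

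**Shift in the group baseline.** If each waived subject has a Day 0 mean GI of g instead of 0.5, the group mean rises by k(g − 0.5)/15. The range g = 1.0 to 2.0 is assumed.

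| k | g = 1.0 | g = 2.0 |
|---|---|---|
| 1 | 0.5/15 = 0.03 | 1.5/15 = 0.10 |
| 3 | 1.5/15 = 0.10 | 4.5/15 = 0.30 |

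At the mild end, one subject with one bleeding site adds only 0.125/15 = 0.008 compared with an all-zero subject.

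**Cost of leaving waived subjects out.** The plan's N = 15 cannot be reproduced, because it gives no effect size, standard deviation, power or dropout. As an illustration, take a paired t-test at two-sided 0.05 with noncentrality d√n. At n = 15, 80% power needs d = 0.778 (0.778 × √15 = 3.01). With that d held fixed, power is 77% at n = 14, 73% at n = 13 and 69% at n = 12. A sensitivity analysis without waived subjects is feasible, but a replaced screen failure loses nothing.

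**What the analysis would correct.** The control quadrant of the same mouth removes a baseline rise that is equal on both sides. It does not remove an asymmetric rise, and it does not restore a healthy start for reading the time course. Covariance adjustment is optional, and no other step deals with waived subjects.

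**The case against.** A reader might infer that the clause breaches the amendment rule. The documents do not support that. The rule governs changes to the protocol, whereas a waiver changes no criterion for anyone else. The clause is itself protocol text that goes to the IRB before the study starts, so the commitment in Quality Assurance/Conduct of the Study ("This clinical research study will be conducted in compliance with this protocol") is not contradicted either. What stands is an uneasy fit with the adherence sentence and the absence of an IRB step for the individual case.

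A reader might also take the power as unconditional. It is not: justification and advance authorisation are real prior conditions, beyond record-keeping. It would be hard to justify scientifically starting induced gingivitis in inflamed gums. But that judgement is left to the sponsor's side, with no criterion placed out of reach.

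Nor do the documents show that Day 0 is the criterion most likely to be waived. The Day -14 work already done by then makes a Day 0 failure costly, but no criterion is named as a candidate. The idea that pregnant women could be enrolled by waiver also fails, given the Pregnancy section.

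Finally, it can be argued that little bias would follow. A waiver admits both quadrants and cannot alter the random assignment. The device is judged against GI and crevicular fluid volume, which are collected at Day 0 and at every later visit, so an inflamed Day 0 site still gives a usable paired reading. This stands for the device comparison and, in part, for test versus control. It does not stand for the healthy reference from which induction and resolution are read.

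**Conclusion.** The point holds as a risk that the protocol leaves open. The clause exempts no criterion, names no IRB step, and has no counterpart in the analysis plan. It reaches the criterion on which the induction-and-resolution aim depends and the medical exclusions.

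It is not a finding that the baseline is compromised, because no waiver is planned. The 6.7% per subject is a share of the sample and does not measure harm. The baseline shifts of 0.03 to 0.30 rest on assumed waiver counts and assumed Day 0 scores, and a mild case would add almost nothing. No stated figure in the plan changes. This is an inexpensive improvement worth making.

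**What to change.** Amend Adherence to Protocol/Amendment(s) in one of two ways: state that the Day 0 gingival-health criterion and the medical exclusions cannot be waived, or delete the two waiver sentences.

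Add that a subject who does not meet the Day 0 criterion is a screen failure, does not begin oral hygiene abstinence, and is replaced within the planned 15. The protocol has no replacement rule at present, so this is an addition as well as a deletion.

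If waivers of other criteria are kept, require IRB notification of each one. State in the Statistical Analysis Plan that results will be reported with and without waived subjects.

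The cost is a short amendment, an occasional subject lost after the Day -14 examination, prophylaxis and stent work, and the screening of a replacement.
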